8.2.2. Secondary Analyses

The secondary endpoints, change from baseline in FVC, muscle strength, timed function tests and patient reported outcome measures, will be analyzed based on the FAS using a mixed effects model with REML estimation. The change over the lead-in period, treatment, time and treatment by time interaction and will be included as fixed effects in the model. The following covariance structures and random effects will be considered: Marginal Unstructured, Marginal Variance Components, Marginal Compound Symmetry, Variance Components with Random Intercept, Unstructured with Random Intercept and Slope, Compound Symmetry with Random Intercept and Slope, Spatial Linear with Random Intercept and Slope. Choice of final model will be based on minimum AIC.

The dependent variable: change from Visit 3 at each *post-baseline interval*, i.e.: Change over post-baseline interval 1: (visit 7 –visit 3) Change over post-baseline interval 2: (visit 11-visit 3) Change over post-baseline interval 3: (Visit 15-Visit 3), for Cohort 1 only Change post-baseline interval 4: (Visit 19-Visit 3), for Cohort 1 only

Covariates are :

- Fixed effects:
 - Baseline interval change (Visit 3 Visit 2)
 - Treatment category (Dose= "5mg/kg", "5 + 40 mg/kg", "20mg/kg" or "40mg/kg")
 - o Time coded as Interval Indicator
 - Treatment category by time interaction
- Random effects:
 - Choice among Marginal Model, Random Intercept Model, and Random Intercept and Slope are selected based on the minimum AIC

Model-estimated change over each post-baseline interval with, 95% two-sided confidence intervals, will be displayed in tabular format.

For each dose level graphical displays will show model-based estimates of change in the mean functional measure from visit 3 at each visit and corresponding confidence intervals derived from the model.

Additionally a completer analysis will also be conducted as a sensitivity analysis for the missing data handling under the mixed effects modeling. The completer analysis will only

include subjects that completed all assessments at the last scheduled visit using the same longitudinal mixed effects model as the primary analysis.

Transformation of the data will be considered if model assumptions are not met.

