## 6.2. Lead-in Period: Visit 2 (Baseline Day -111 to -110 prior to dosing on Day 1)

The following procedures and studies should be performed in the morning (before noon) of Visit 2 whenever possible

- Physical Examination, including Nose and Throat Mucosal Exam
- **Pregnancy Test**: A highly sensitive urine pregnancy test will be performed on all female subjects and must be confirmed as negative within 1 month of receiving first dose.
- Diary Cards: For collection of first day of each menstrual cycle for WOCBP.
- Contraception Review: Confirmation of use of acceptable forms of contraception
- Height: Height should be measured in the morning.
- Weight
- Vital signs: Supine blood pressure, pulse rate, respiratory rate, and oral temperature.
- Horomone Testing: LH, FSH, estrogen in WOCBP
- GLDH
- C-SSRS
- **MRI-muscle:** WB-MRI and dedicated thigh MRI will be performed for muscle quantity and quality

The following procedures should be performed in the afternoon of Visit 2 whenever possible:

- **DXA:** Whole body DXA will be performed for lean body mass.
- **Functional assessments:** Must be conducted in the following order: Respiratory function (FVC, FEV1, MIP, MEP), 4SC, 2MWT, 10-meter walk/run, TUG, strength assessment (MMT, hand-held dynamometry) and PUL.
- **Needle muscle biopsy:** Following WB-MRI and functional assessments a needle muscle biopsy of the tibialis muscle will be performed.
- PD sample collection

- **Biomarker collection:** Blood will be collected for proteomic, metabolomic, and genomic biomarker analysis
- Adverse event monitoring
- Concommitant medications

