#### **Prior to dosing, the following procedures will be completed:**

- Physical Examination, including Nose and Throat Mucosal Exam
- **Pregnancy Test**: A highly sensitive urine pregnancy test will be performed on all female subjects
- Diary Cards: For collection of first day of each menstrual cycle for WOCBP.
- Contraception Review: Confirmation of use of acceptable forms of contraception
- Weight
- Vital signs: Supine blood pressure, pulse rate, respiratory rate, and oral temperature.
- **12-lead ECG:** ECGs will be performed in triplicate
- Clinical laboratory tests:
  - Hematology with complete blood count and differential, comprehensive metabolic panel (sodium, potassium, chloride, carbon dioxide, blood urea nitrogen, creatinine, calcium, glucose, total protein, albumin, total bilirubin, AST, ALT, alkaline phosphatase) gamma-glutamyl transferase (GGT), prothrombin time (PT), activated partial thromboplastin time (aPTT), creatine kinase, amylase, cardiac troponin I. Urinalysis.
- Serum ferritin, serum iron, % transferrin saturation, TIBC: fasting blood collection
- Horomone Testing: LH, FSH, estrogen in WOCBP
- GLDH
- **Fecal occult blood**: Fecal sample is to be collected at home within 1 week prior to scheduled visit.
- C-SSRS

- Immunogenicity: Baseline
- PD sample collection: Predose
- PK sample collection: Predose
- **MRI-liver**: Liver MRI will be obtained for iron accumulation (visit 11 only)
- **MRI-muscle:** WB-MRI and dedicated thigh MRI will be performed for muscle quantity and quality
- **DXA Whole Body:** Whole body DXA will be performed for lean body mass.
- **DXA Spine and Hip:** Spine and hip DXA will be performed for BMD.
- **Functional assessments:** Must be conducted in the following order: Respiratory function (FVC, FEV1, MIP, MEP), 4SC, 2MWT, 10-meter walk/run, TUG, strength assessment (MMT, hand-held dynamometry) and PUL.
- Quality of Life assessments
  - InQol
  - SF-36

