#### After dosing, the following procedures will be completed:

- Vital signs: Supine blood pressure, pulse rate, respiratory rate, and oral temperature after completion of infusion. Infusion site reaction monitoring.
- AE monitoring.
- Concomitant medication monitoring.
- 6.7. Active Treatment: Visit 7 (Day 113±3) and for Cohort 1, Visit 15 (Day 337±3)
  - **Pregnancy Test**: A highly sensitive urine pregnancy test will be performed on all female subjects
  - Diary Cards: For collection of first day of each menstrual cycle for WOCBP.
  - Contraception Review: Confirmation of use of acceptable forms of contraception
  - Weight
  - Vital Signs: Supine blood pressure, pulse rate, respiratory rate, and oral temperature.
  - Clinical laboratory testing:
    - Hematology with complete blood count and differential, comprehensive metabolic panel (sodium, potassium, chloride, carbon dioxide, blood urea nitrogen, creatinine, calcium, glucose, total protein, albumin, total bilirubin, AST, ALT, alkaline phosphatase) gamma-glutamyl transferase (GGT), prothrombin time (PT), activated partial thromboplastin time (aPTT), creatine kinase, amylase, cardiac troponin I. Urinalysis.
  - Serum ferritin, serum iron, % transferrin saturation, TIBC: fasting blood collection
  - GLDH
  - **Fecal Occult Blood:** Fecal sample is to be collected at home within 1 week prior to scheduled visit.
  - C-SSRS
  - PK/PD sample: predose

- **Biomarker collection:** Blood will be collected for proteomic, metabolomic, and genomic biomarker analysis
- **Functional assessments:** Must be conducted in the following order: Respiratory function (FVC, FEV1, MIP, MEP), 4SC, 2MWT, 10-meter walk/run, TUG, strength assessment (MMT, hand-held dynamometry) and PUL.

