8. STATISTICAL METHODOLOGY AND STATISTICAL ANALYSES

Continuous variables will be summarized by the number (N), mean, median, standard deviation, minimum and maximum. Categorical variables will be summarized by percent and counts. All summaries will be displayed by treatment. Efficacy data will be listed, tabulated and graphically represented, as appropriate.

All analyses will be based on the full analysis set (FAS) which includes all enrolled subjects who have received at least one dose of study drug.

Below is outlining the definition of baseline for secondary endpoints :

As per Figure 1 below shows each treatment period has been divided into 16 week intervals. Endpoint is the change from the baseline to the subsequent 16th week.

A placebo group is constructed by combining the 3 cohort's running periods. Each cohort has an initial 16 week running period, they are combined together to form a placebo group which will be used as a comparison group, testing against active treatments. There will be a total of 20 subjects in the placebo group.

For cohort 1 the first comparison would be : placebo (3 cohort's running periods) vs. active treatment (1^{st} interval) which starts from the end of the running period to the end of the first 16 weeks of active treatment i.e. week 17 to week 32. The next comparison would be placebo

vs. active treatment (second interval) which starts from the end of the second 16 week active treatment i.e. week 33 to week 48. Then the next comparison would be placebo vs. active treatment (third interval) i.e. week 49 to week 64. Finally comparing placebo vs. active treatment (fourth interval) i.e. week 65 to week 80, as shown in the table 1 below.

The above rational is to be used for cohorts 2 and 3.

To conclude there will be 8 statistical tests.

Active treatment Intervals				
Cohort 1	Cohort 2	Cohort 3		
17-32	17-32	17-32		
33-48	33-48	33-48		
49-64				
65-80				

[figure not shown]

Figure 1. LGMD2i Active vs. "Placebo"

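### SAP 8.2.2 models InQoL and SF-36 with a lead-in covariate that is scheduled for none of the 20 subjects, and Appendix 1 plans no such output

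*SAP*

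**What the plan says.** SAP 8.2.2 starts its list of secondary endpoints with FVC and muscle strength and ends it: "timed function tests and patient reported outcome measures, will be analyzed based on the FAS using a mixed effects model with REML estimation". The patient-reported outcomes are InQoL and SF-36 (SAP 4.2.2.4 and 6.2.1).

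The first fixed effect is "Baseline interval change (Visit 3 Visit 2"; the minus sign has evidently been lost, since the paragraph above it describes the change over the lead-in. The others are treatment category, interval and their interaction. The responses are the changes from Visit 3 to Visits 7 and 11 in all cohorts, and to Visits 15 and 19 in Cohort 1. The promised output is: "Model-estimated change over each post-baseline interval with, 95% two-sided confidence intervals, will be displayed in tabular format".

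SAP section 8 introduces its comparison plan with "Below is outlining the definition of baseline for secondary endpoints". It pools the lead-in periods of the three cohorts: "they are combined together to form a placebo group which will be used as a comparison group, testing against active treatments". It counts 20 subjects in that group and eight tests. It neither names nor excepts the questionnaires.

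Protocol 9.2.1 and 9.2.2 describe a longitudinal model adjusted for the baseline result and extend it to the quality-of-life questionnaires.

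**The concern.** A model needs its covariate and its responses to be measured. The lead-in change requires a questionnaire at Visit 2, and two of the four responses require one at Visit 7 or 15. If the schedule has none there, the stated analysis returns nothing for InQoL and SF-36, and the analyst has to choose another covariate, other responses and other fixed effects outside the SAP.

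These are self-reported outcomes in an open-label study, so that choice should not be left until the data are in hand. The documents also point to different replacements: 8.2.2 to modelled changes with confidence intervals, Appendix 1 to summaries and a listing, and the protocol to a baseline-adjusted model.

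**Working it through.** **1. The plan's own counts.** Lead-in subjects: 4 + 8 + 8 = 20. Active intervals tested: 4 + 2 + 2 = 8. Both agree with SAP section 8.

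**2. Rows the 8.2.2 model needs, assuming full attendance.** Cohort 1: 4 subjects × 4 intervals = 16. Cohort 2: 8 × 2 = 16. Cohort 3: 8 × 2 = 16. Total 48.

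**3. Visits needed, set against the schedule.** Sources are Schedule of Activities Tables 1 and 2 and the visit lists in protocol section 6.

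| Visit | Role in the model | InQoL and SF-36 scheduled? |
|---|---|---|
| 2 | lead-in covariate | No (blank in both tables; absent from 6.2) |
| 3 | reference for every change | Yes (6.3) |
| 7 | interval 1 | No (blank; absent from 6.7) |
| 11 | interval 2 | Yes (6.3 for Cohort 1, 6.8 for Cohorts 2 and 3) |
| 15 (Cohort 1) | interval 3 | No (blank; absent from 6.7) |
| 19 (Cohort 1) | interval 4 | Yes (6.8) |

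The text confirms the tables, so the blanks are not a conversion fault. The Visit 2 list, including the part headed "The following procedures should be performed in the afternoon of Visit 2 whenever possible", has no questionnaire. Nor has the section headed "Active Treatment: Visit 7 (Day 113±3) and for Cohort 1, Visit 15 (Day 337±3". The Visit 3 list does, under "Quality of Life assessments".

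**4. What is left.**

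| | InQoL, SF-36 | FVC and functional tests |
|---|---|---|
| Subjects with the covariate | 0 of 20 | 20 of 20 |
| Responses at Visits 7 / 11 / 15 / 19 | 0 / 20 / 0 / 4 | 20 / 20 / 4 / 4 |
| Response rows | 24 of 48 | 48 of 48 |
| Rows usable as written | 0 of 48 | 48 of 48 |

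The fault is specific to the questionnaires. The completer analysis uses the same model and fails in the same way. If the eight lead-in tests of section 8 are meant to cover the questionnaires, none can be formed.

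**5. Whether another provision rescues the model.** None does. Minimum AIC chooses the covariance structure and random effects, not the fixed effects. SAP section 7 relies on maximum likelihood and the developers' guidance, and neither supplies a covariate that is absent by design for everyone. The unscheduled-visit list (protocol 6.14) has no questionnaire.

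**6. Whether dropping the covariate is enough.** It is not. The 24 rows fall in four cells: 5, 20 and 40 mg/kg at Visit 11, and 5 + 40 mg/kg at Visit 19. The design has rank 4 with treatment alone, rank 4 with treatment and time, and rank 4 with the interaction as well. Time and interaction therefore add no estimable parameter. For the functional tests the same ranks are 4, 6 and 8.

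**7. Whether a reduced model can be fitted.** Four cell means plus the Visit 3 score give a 24 × 5 design of rank 5, with 24 − 5 = 19 residual degrees of freedom (t = 2.093). With a common residual SD and Cohort 1's two records treated as independent, the median 95% half-widths over 4000 simulated sets of Visit 3 scores were 0.745 SD for 8 subjects and 1.057 SD for 4. As a check at Visit 11 alone, 20 − 4 = 16 degrees of freedom (t = 2.120) give 2.120/√8 = 0.75 and 2.120/√4 = 1.06.

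**8. Appendix 1.** Mixed-model tables are 14.1.1.65–66, 69–70, 75–76, 79–80, 83–84, 87–88, 91–92, 95–96, 99–100 and 103–104: 10 pairs, or 20 tables for 10 endpoints. The six questionnaire items (14.1.1.107–112) are an InQoL total score, four InQoL symptom summaries and an SF-36 listing. None is titled as a mixed model or a change from baseline, although the endpoint is a mean change from baseline.

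**The case against.** The strongest reply is that the model was written for the functional tests and the questionnaires were swept in by one phrase. Appendix 1 plans only summaries and a listing for them, and the graphics sentence in 8.2.2 speaks of a functional measure. On that reading, deleting the phrase is enough. The failure would also show itself at programming, since a model with no usable rows cannot give a wrong estimate. This is a fair account of the likely intent and it limits the harm. It does not settle which SAP statement governs, and a reader cannot tell from the document.

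Three narrower points stand in part:

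- **Protocol 9.2.2.** Protocol section 9 lets the SAP modify secondary analyses, so the binding conflict is within the SAP, between 8.2.2 and Appendix 1.
- **The reduced model.** It shares the protocol's principle of adjusting for baseline but is not the protocol's model, because time and interaction drop out. Protocol 6.2 also labels Visit 2 as baseline; the use of Visit 3 as reference comes from the SAP.
- **The 1.06 SD half-width.** It is optimistic for Visit 19. If that visit's variance is estimated from its four subjects alone, a simple mean gives 3.182/√4 = 1.59 SD.

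Applying the eight lead-in tests to the questionnaires is a reading of general wording, not something section 8 states.

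**Conclusion.** The concern holds. As written, the 8.2.2 model gives no result for InQoL or SF-36: 0 of 20 subjects have the covariate and 0 of 48 rows are usable. This follows from the schedule and needs no assumption about variance or effect size; the count of 24 collected responses assumes full attendance. Appendix 1 contradicts the promised output, with no mixed-model table among six questionnaire items.

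The consequence is an unspecified replacement analysis for one secondary endpoint family. Descriptive change from Visit 3 remains possible. This should be corrected, but it does not threaten the trial's main conclusion. The half-widths show only what a replacement could deliver; the finding does not depend on them.

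**What to change.** Adopt one of two changes in the SAP.

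**If a model is wanted**, add to 8.2.2: *For InQoL and SF-36 the response is change from Visit 3 to Visit 11 (all cohorts) and to Visit 19 (Cohort 1). The Visit 3 score replaces the lead-in change as covariate. Only the four observed treatment-by-visit means are estimated, with 95% confidence intervals. These outcomes have no untreated lead-in comparator.* State how the variance at Visit 19 and the correlation between Cohort 1's two records are handled. Exclude the questionnaires from the eight tests in section 8, and add change-from-baseline tables for both instruments to Appendix 1.

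**If description is intended**, remove the patient-reported outcomes from the model sentence in 8.2.2, except them from the section 8 tests, and add descriptive change-from-Visit 3 tables so that the stated endpoint is reported.

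The cost is one SAP paragraph and about two tables, with no new data collection. The drawbacks are an explicit loss of the lead-in comparison for these outcomes and, under the model, wide intervals: about 0.75 SD either side for an 8-subject cohort and 1.06 SD or more for the 4-subject cohort.

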#### 9.2.1. Analysis of Primary Endpoint

Change from baseline in FVC will be analyzed using a longitudinal mixed effects model. The baseline result, treatment, time and treatment by time interaction will be included as fixed effects in the model. Subject will be included as a random effect and the model will be fit with an unstructured covariance for the repeated measures. Additionally, non-Gaussian models may be explored in the case of non-normal data for the FVC.

Missing data will be imputed using maximum likelihood techniques for a mixed effects model. This analysis is unbiased under the assumption of missing at random when the model assumptions hold. Subjects who lose motor functions (e.g. TUG, 2MWT) will be regarded as missing not at random. Additional imputation methods to assess the sensitivity of the analysis to missing not at random data may also be performed. A completer analysis will also be conducted as a sensitivity analysis.

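### SAP 8.2.2: with four subjects at intervals 3 and 4, the Marginal Unstructured candidate has an unbounded REML likelihood, and the minimum-AIC rule does not exclude it

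*SAP*

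**What the plan says.** SAP 8.2.2 analyses change from Visit 3 "using a mixed effects model with REML estimation". The fixed effects are the lead-in change, treatment category, interval, and "Treatment category by time interaction". Two of the four intervals exist in one cohort only: "Change over post-baseline interval 3: (Visit 15-Visit 3), for Cohort 1 only" and "Change post-baseline interval 4: (Visit 19-Visit 3), for Cohort 1 only". SAP 2.1 plans Cohort 1 at 4 subjects and Cohorts 2 and 3 at 8 each.

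Seven structures are candidates. The list opens with "Marginal Unstructured, Marginal Variance Components, Marginal Compound Symmetry" and goes on to four versions with random effects. The rule for choosing among them is "Choice of final model will be based on minimum AIC". Model estimates for each interval are reported with "95% two-sided confidence intervals".

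Neither SAP 8.2.2 nor SAP 7 (missing values) says what happens if a fit does not converge or is singular. No order of structures is given. The only contingency in 8.2.2 is to consider transforming the data.

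Protocol 9.2.1 describes a different model for FVC: "Subject will be included as a random effect and the model will be fit with an unstructured covariance for the repeated measures". It has no fallback either.

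**The concern.** An unstructured 4x4 covariance has 10 parameters, and everything it says about intervals 3 and 4 must come from four people. When a model has enough freedom to reproduce those observations exactly, its likelihood can be raised without limit by shrinking a variance towards zero. A rule that takes the smallest AIC then rewards the degenerate fit, because the penalty is fixed and the gain is not.

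At stake are the model-based estimates and intervals for Cohort 1 at intervals 3 and 4. These carry the 5 + 40 mg/kg category, the longest exposure in the main study. FVC, which protocol 1.11 calls a high-priority outcome, is among the endpoints affected. If the software stops or the analyst discards the fit, the replacement is chosen after the data are seen, in an open-label study, under no written rule.

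**Working it through.** The documents give no variance, power or sample-size figure for this analysis, so there is no stated number to reproduce. The central result needs only counting. The simulations rest on assumed variances.

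**Inputs.** Subjects 4, 8 and 8 (SAP 2.1). Intervals 1 to 4 for Cohort 1, and 1 to 2 for Cohorts 2 and 3 (SAP 8.2.2). Observations: 4×4 + 8×2 + 8×2 = 48. Fixed effects: 4 + 2 + 2 = 8 cell means plus one common lead-in slope = 9.

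**Step 1: counting.** After the interval-4 mean is fitted, 4 subjects leave 4 − 1 = 3 contrasts. The unstructured model has 3 free coefficients for interval 4 given intervals 1 to 3, so the fit is exact. Let d be the conditional variance of interval 4 given the other three. As d goes to 0:

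- the four subjects' log-determinants contribute 4 log d to −2 REML log-likelihood;
- the interval-4 mean gives back one log d, and the common lead-in slope gives back at most one more;
- the residual term does not grow, because the fit is exact.

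So −2REML falls at least as fast as (4 − 1 − 1) log d = 2 log d, without a floor. Without the lead-in covariate the rate is 3 log d.

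**Step 2: numerical check.** One simulated data set (unit variance, correlation 0.6, no dropout) was profiled over log d:

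| log d | 0 | −2 | −4 | −6 | −8 | −10 | −12 |
|---|---|---|---|---|---|---|---|
| −2REML | 78.9 | 72.9 | 66.9 | 61.2 | 56.1 | 51.9 | 47.8 |

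The last steps are close to 2 × 2 = 4, as the count predicts. In a data set fitted without the covariate, −2REML fell from 112.6 to 76.6 over the same six steps: 36/6 = 6 per step, matching 3 × 2.

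**Step 3: AIC.** AIC = −2REML + 2 × (covariance parameters). The penalty is 20 for unstructured (10 parameters), 4 for compound symmetry (2), and 8 each for separate interval variances (4) and random intercept and slope (4). In all 10 simulated data sets, unstructured fell below the best of these three by log d = −6 at the latest, for example 92.8 against 96.8 and 109.4 against 115.8. In seven it kept falling down to log d = −18. In the other three it was already 54 to 68 below the best competitor at log d = −2, then rose at smaller d. Step 1 rules out a true rise towards d = 0, so these are optimiser failures. An analyst would meet both outcomes: a singular winner or a failed fit.

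**Step 4: controls.** With 6 or 7 Cohort 1 subjects the profile had an interior minimum (with 6: 111.3, 103.4, 108.7 at log d = 0, −2, −4). With intervals 1 and 2 only, it was bounded. InQoL and SF-36 are scheduled at Visits 3, 11 and 19 but not 7 or 15, so only intervals 2 and 4 exist. Their 2x2 unstructured model was bounded with 4 subjects: 73.4, 69.2, 76.0. That run omitted the lead-in covariate, since these questionnaires are not scheduled at Visit 2.

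**Step 5: if the unstructured fit is dropped.** Coverage of the 95% interval at interval 4, in the 4/8/8 design with error SD 1:

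| Assumed slope SD ÷ error SD | AIC choice | Random intercept and slope singular or nearly so |
|---|---|---|
| 0 | 96% | 73% of trials |
| 0.3 | 92% | 63% |
| 0.6 | 86% | 54% |

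Each row is 250 runs. Two other sets of 150 runs at 0.6 gave 90% and 91% for AIC choice (the second between compound symmetry and random intercept and slope only). They gave 84% and 76% for compound symmetry used throughout, and 95% in both for random intercept and slope. Monte Carlo standard errors: √(0.90×0.10/150) = 2.4 points and √(0.86×0.14/250) = 2.2 points.

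**Step 6: protocol 9.2.1.** A random subject effect adds one constant to all elements of a matrix that is already unrestricted. That is 11 parameters for 10 elements, so the two parts cannot be separated. The marginal model is the same unstructured one.

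**The case against.** The strongest reply is that the rule still works in practice. Seven structures are listed. If one fails, six remain, and those fitted in the check had finite AIC. A competent analyst would not report a singular covariance, and SAP 8.1 foresees assessing goodness of fit. A reader might infer from the unbounded likelihood that the plan cannot yield any valid model. The documents do not support that. What stands is narrower: no sentence excludes a singular fit, so discarding it is an unwritten decision.

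A reader might also infer that both candidates with unstructured in their name should go. The label combining it with random intercept and slope is ambiguous. If it describes the residual matrix, the same defect applies and the model is over-parameterised. If it describes a 2x2 random-effects matrix with independent residuals, it is estimable and is the sensible main model. It needs clarifying, not deleting.

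The coverage evidence is fairly challenged too. The data were generated with random slopes, which favours a random-slope model, and no document gives the slope SD. At slope SD 0 there was no shortfall. Random intercept and slope is itself often singular in this design, so it cannot be named without a fallback. A fallback to random intercept alone would bring back compound symmetry, the structure with the poorest coverage.

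Finally, protocol section 9 lets the SAP modify the protocol's analysis, and descriptive change summaries are planned alongside the model. Both points lower the severity. Neither repairs the rule.

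**Conclusion.** The point holds for FVC and other lung function, strength, timed tests and PUL. With four Cohort 1 subjects, Marginal Unstructured has no finite REML optimum, so minimum AIC as written selects a singular fit or meets a failed one. This depends only on the planned cohort size and visit pattern. Any Cohort 1 dropout makes it worse.

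Two wider conclusions do not follow. Not every secondary endpoint is affected, since InQoL and SF-36 escape through their visit schedule. Nor can one say that the reported intervals will be too narrow. They may be, with interval-4 coverage of roughly 86 to 91% under AIC choice, if slopes vary by about 0.6 of the error SD. Coverage was about 92% at 0.3 and 96% at 0, and which case applies is unknown.

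Severity: should be fixed before analysis. The primary endpoint is safety, and these are secondary estimates.

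**What to change.** In SAP 8.2.2:

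- Remove Marginal Unstructured for the four-interval endpoints, or restrict it to intervals 1 and 2.
- State that the unstructured candidate with random intercept and slope means an unstructured 2x2 random-effects matrix with independent residuals.
- Pre-specify that model, with Kenward-Roger degrees of freedom, as the main analysis in place of selection by AIC.
- State that a non-converged or singular (boundary) fit triggers a fixed fallback order that still lets variance differ by interval: for example, uncorrelated random intercept and slope, then separate variances by interval. Homogeneous compound symmetry or random intercept only comes last, flagged as possibly too narrow at intervals 3 and 4.

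Align protocol 9.2.1, whose random subject effect plus unstructured covariance is not identifiable.

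The cost is wording, with no new data or visits. The downside is slightly less covariance flexibility at intervals 1 and 2.
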